## Project Details

### I. Project Introduction

**I.1** *Project to be reviewed by:*  
IRB-01

**I.2** *Project Title:*  
Evaluating racial and ethnic differences in micropore closure using optical coherence tomography

**I.3** *Short Title (optional):*  
Visualizing micropore closure with OCT

**I.4** *Provide a short summary of the purpose and procedures of the study proposed in this IRB application.*

- ***DO NOT include information on studies not proposed in this application.***
- ***Use LAY terminology only. This must be easily understandable by IRB community members and nonscientists.***
- ***DO NOT cut and paste technical abstracts from funding applications that may not be understood by a general audience.***

The purpose of this study is to use an innovative, noninvasive imaging technique called optical coherence tomography (OCT) to visualize micropore closure in racial/ethnic skin following micropatch application. Healthy and consenting adult volunteers (18-45 years old) will be enrolled. Subjects will be asked to self-identify their race and ethnicity according to the following groups: Black, Asian, Latinx, White, Indigenous, or Bi-/multi-racial/other. All subjects, regardless of self-identified race/ethnicity, will receive the same micropatch treatment and measurements. The micropatches are patches containing a small array of microneedles on an adhesive patch backing; the whole micropatch fits on the tip of a thumb. The micropatches will be applied to the upper arm, forearm, and the palm. At each of these locations, 3 sites will be identified. One site will receive micropatch application followed by occlusion with a small patch (note: this is just a band-aid like patch, not a micropatch). The other 2 sites will be controls: one site will be treated with a micropatch but will not be covered afterwards, and the other site will be an occlusion control site (covered with an occlusive patch but no micropatch application). Noninvasive measurements will be made at baseline to determine

differences in hydration, skin water loss, electrical resistance (impedance), and color between subject groups. OCT scans will be made on the skin to noninvasively visualize the skin structure, allowing calculations of epidermal thickness and microvasculature density. After the micropatch is applied to one site at each of the 3 body locations, the water loss, impedance, and OCT measurements will be repeated. The micropatches are only applied on the first study day.

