## VI. Subjects

VI.1 *How many adult subjects do you expect to consent or enroll for this project?*  
100

VI.2 *What is the age of the youngest adult subject?*  
18.0

VI.3 *What is the age of the oldest adult subject?*  
45.0

VI.4 *What is the percentage of adult male subjects?*  
50

VI.5 *What is the percentage of adult female subjects?*  
50

VI.6 *How many minor subjects do you expect to consent or enroll for this project?*  
0

VI.13 *Describe EACH of your subject populations*

- *Include description of any control group(s)*
- *Specify the Inclusion/Exclusion criteria for EACH group*

There will be no control group for this study.

Inclusion Criteria: Subjects will be healthy men and women between 18 and 45 years of age.

Exclusion Criteria:

- 1) Unable to give consent
- 2) Severe general allergies requiring chronic treatment with steroid or antihistamines
- 3) Previous adverse reaction to microneedle insertion
- 4) History of keloids
- 5) Known allergy or adverse reaction to medical tape/adhesive, or aloe vera
- 6) Any inflammatory diseases of the skin (including but not limited to: psoriasis, atopic dermatitis, and blistering skin disorders)

- 7) Any disease associated with altered immune function (including but not limited to: rheumatoid arthritis, diabetes, lupus, HIV/AIDS)
- 8) Any subject taking medication that impairs the immune system (including but not limited to corticosteroids, TNF inhibitors, monoclonal antibodies, chemotherapy agents)
- 9) Any current malignancy or history of malignancy present at the treatment sites
- 10) Eczema or scaling present at any treatment site; any current inflammation or irritation present at the treatment sites (including but not limited to: rash, inflammation, erythema, edema, blisters)
- 11) Uncontrolled mental illness that would, in the opinion of the investigator, affect the subject's ability to understand or reliably participate in the study

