First name, Last name, Preferred name, preferred pronouns

Are you between 18 and 45 years of age?

What race or ethnicity do you identify with (subject will be provided with the following options: Black, Asian, Latinx, White, Indigenous, bi-/multiracial or More Options)

Do you take any prescription medications (excluding birth control)?

Do you have any chronic or ongoing medical conditions (including skin disorders or pregnancy)?

Do you have any general allergies that require daily treatment with steroids and antihistamines?

Do you have a known allergy or adverse reaction to medical tape, band-aids, adhesive or aloe vera?

Contact information: number, email address

What type of contact do you prefer: phone/email

Prior to consent individuals will complete the pre-screening questionnaire either in paper form (attached doc: 202010229\_PreScreeningQuestionnaire\_v1) or electronically (attached document: 202010229\_RedCap\_PreScreeningSurvey\_v2).

**VII.D.21** *Will you keep a screening log or other record that would include information on people who do not enroll in the study?*  
Yes

**VII.D.22** *Describe the information being collected and the purpose for keeping this information.*  
A screening log will be maintained that will document the first and last name of the prospective participant that was screened, date of screening, phone number (if provided), email address (if provided), and whether it was a screen failure or if the subject will continue on to the consent process. This information will be kept until all study activities have been completed for all participating subjects. We will keep the screening information because it is not uncommon for individuals to respond to the same advertisements more than once (for example, Noon News) and we want to know if a subject has previously contacted us about the study. The log will be destroyed after completion of the study for enrollment in future studies.

**VII.D.23** *Will this information be shared with anyone outside the UI research team members?*  
No

**VII.D.25** *After the subject agrees to participate (signs consent), are there any screening procedures, tests, or studies that need to be done to determine if the subject is eligible to continue participating?*  
Yes

**VII.D.26** *List and describe screening*  

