**VII.D.29 *Provide a description of the enrollment and consent process for adult subjects***

- **Describe each study population separately including control population**
- **Include when recruitment and consent materials are used**
- **Use 3rd person active voice “The Principal Investigator will identify subjects. For example, the principal investigator will identify potential subjects, the study coordinator will discuss the study with subjects over the telephone and schedule the first study visit, etc...”**
- **Describe the steps that will be taken by the research team to minimize the possibility of coercion or undue influence during the consent process**

Participants in this study will be normal healthy individuals aged 18-45. All participants will act as their own controls.

This study will be advertised through the University of Iowa campus-wide email system and through the University of Iowa Health Care “Noon News,” a daily announcement flier for community and faculty members within the UIHC. Advertisements for this study have been created so that specific subject populations may be better reached via targeted advertisements, in order to meet our enrollment goals. (attached docs: 202010229\_MassEmail\_v1; 202010229\_NoonNews\_v1)

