## **XI. Data Analysis**

**XI.1** *Describe the analysis methods you will use, including, if applicable, the variables you will analyze*  
Paired t-tests will be performed to compare impedance and TEWL measurements pre- and post-micropatch treatment at each site. Influence of skin color and self-reported ethnicity/race on measured parameters will be compared using one-way ANOVA. Micropore closure kinetics will be calculated by modeling the data and calculating a micropore closure half-life. Epidermal thickness, skin roughness, and microvasculature density will be calculated by the OCT software and compared between groups using one-way ANOVA. For all analyses,  $p < 0.05$  will be considered statistically significant. GraphPad Prism Software (GraphPad Software, San Diego, CA) or Microsoft Excel will be used for statistical analyses.

**XI.2** *Provide the rationale or power analysis to support the number of subjects proposed to complete this study.*  
This is a pilot study that does not require a power analysis because data regarding the variability in parameters measured via OCT in racial/ethnic groups is not available. We are targeting 20 subjects per group because this is a reasonable number of subjects for a pilot.

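### Twenty per group and 100 in total fit five groups, but the plan lists six (or seven) and never says which ones are compared

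*Combined protocol and SAP*

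**What the plan says.** Section XI.2 declines a power analysis on the ground that "data regarding the variability in parameters measured via OCT in racial/ethnic groups is not available", and continues: "We are targeting 20 subjects per group because this is a reasonable number of subjects for a pilot". Read together, the two sentences make a group a racial/ethnic group. No other meaning is available: VI.13 says there is no control group, VII.E.1 says there is no randomization, and I.4 gives every subject the same treatment.

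The other relevant statements are:

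- **I.4** has subjects "self-identify their race and ethnicity according to the following groups: Black, Asian, Latinx, White, Indigenous, or Bi-/multi-racial/other". That is six categories, and the section itself calls them groups.
- **VII.D.20** (screening question): "subject will be provided with the following options: Black, Asian, Latinx, White, Indigenous, bi-/multiracial or More Options". This is six options, or seven if More Options is separate from bi-/multiracial.
- **VI.1** asks "How many adult subjects do you expect to consent or enroll for this project", and the answer is 100.
- **VII.D.29** says that "specific subject populations may be better reached via targeted advertisements, in order to meet our enrollment goals", but gives no goal for any group.
- **XI.1**: "Influence of skin color and self-reported ethnicity/race on measured parameters will be compared using one-way ANOVA". The levels of the race/ethnicity factor are not listed.

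**The concern.** The per-group number, the total and the list of groups do not agree. The per-group number is also the only justification offered for the study's size, and the groups it refers to are the levels of the race/ethnicity ANOVAs. Racial and ethnic differences are in the study's title, so a reader should be able to tell how many groups are compared and how large each is meant to be.

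Two things are at stake. Recruitment has no workable per-group target, because 20 in each listed group cannot be reached within 100. And because the levels of the ANOVA are not named, categories could be kept, merged or dropped once enrolment is known. That is a risk of leaving the point open; nothing in the documents suggests that it is planned.

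The paired pre/post comparisons and the skin-color comparison do not take their levels from this list and are not affected.

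**Working it through.** **Inputs.** Target per group: 20 (XI.2). Total consented or enrolled: 100 (VI.1). Number of groups k: 6 (I.4), or 6 to 7 (VII.D.20). The plan gives no SD, effect size, power or loss rate.

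**Step 1: can 100 be reproduced?** Required total = 20 × k.

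| k | 20 × k | 100 / k |
|---|---|---|
| 4 | 80 | 25.0 |
| 5 | 100 | 20.0 |
| 6 | 120 | 16.7 |
| 7 | 140 | 14.3 |

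Only k = 5 returns 100 without a further assumption. Four groups with 20% loss would also do so (80 / 0.80 = 100), but the plan states neither input.

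**Step 2: the shortfall with the listed groups.** For six groups, 120 − 100 = 20 subjects too few. Spread evenly, 100 / 6 = 16.7 (in whole subjects, 4 × 17 + 2 × 16 = 100), and (20 − 16.7) / 20 = 17% below target. For seven groups, 100 / 7 = 14.3, which is 29% below.

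**Step 3: the five-group reading.** 100 − 5 × 20 = 0. Every person in the mixed/other category who enrolls within the 100 takes a place from one of the five targeted groups.

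**Step 4: what this does to precision.** The yardstick is the 95% half-width for a difference between two group means, in SD units, with equal groups, the pooled ANOVA error and no multiplicity adjustment: t(0.975, N − k) × √(2/n), where n = N / k.

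- N = 120, k = 6: t(114) = 1.981; 1.981 × √(2/20) = 0.63
- N = 100, k = 6: t(94) = 1.986; 1.986 × √(2/16.67) = 0.69
- N = 100, k = 7: t(93) = 1.986; 1.986 × √(2/14.29) = 0.74
- N = 100, k = 5: t(95) = 1.985; 1.985 × √(2/20) = 0.63

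**Step 5: enrolled against completing.** VI.1 counts people who consent or enroll. The question that XI.2 answers asks about "the number of subjects proposed to complete this study". If 20 means completers, even five groups require that nobody is lost. VII.E.6 foresees both removal after consent and early drop-out, although the pre-screening in VII.D.29 should keep removals low. For an assumed loss of 5% to 15%, 95 to 85 of the 100 complete:

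- five groups: 19 to 17 per group, half-width 0.64 to 0.68 SD
- six groups: 15.8 to 14.2 per group, half-width 0.71 to 0.75 SD

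**The case against.** The best answer is that five groups is the natural reading. Five categories are named singly, the sixth is a catch-all, and 5 × 20 is exactly 100. On that view the plan has left out one clause rather than made an arithmetic error. The figures are also planning numbers, a target and an expectation, and no category is capped. This is plausible and may well be what the investigators meant. But it has to be inferred, I.4 calls all six categories groups, and it does not say how the sixth is recruited, counted or analysed.

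A second objection is that the size of the problem is measured on a scale the plan does not use. XI.1 names no pairwise contrasts or intervals, and the study is a pilot that makes no power claim. That is fair. The half-widths only show how large the mismatch is, and it is small.

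Third, the completer argument rests on the form's standard question and on loss rates that the plan does not give. It is therefore secondary, and the mismatch stands without it.

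Fourth, the explicit hypothesis in I.5, that OCT complements impedance, does not depend on the number of groups. That limits the reach of the point to the race/ethnicity comparisons.

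Finally, the recruitment attachments were not supplied and might name target populations. Even so, the application's own sections should agree with each other.

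**Conclusion.** The concern holds and is minor. As written, 20 per group across the six groups in I.4 requires 120 subjects, and VI.1 provides 100. An even spread over six, which is an assumption, gives about 16.7 per group and widens the pairwise half-width by about 0.06 SD (0.688 − 0.626). If five groups were intended, precision is as implied, but that intention is not stated in the text supplied and there is no allowance for the mixed/other category. The practical gap is the undefined set of groups for the race/ethnicity ANOVAs, more than the lost precision.

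**What to change.** Without enrolling more people, do one of the following:

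1. Restate XI.2 as about 16 to 17 enrolled per group across the six listed groups, and note that slightly fewer may complete.
2. Name in advance the five groups to be compared by one-way ANOVA, with a target of up to 20 enrolled in each. Report the remaining category descriptively, and say that its subjects count within the 100. The words up to matter here, because the five groups cannot all reach 20 once anyone in the remaining category enrolls.

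In either case, say where the More Options answer in VII.D.20 falls, and make I.4, VI.1, VII.D.20 and XI.2 agree.

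The cost is one or two sentences in XI.2 and matching wording elsewhere. The downside is that either the stated number per group or the number of groups compared becomes slightly less favourable. Choosing to describe the mixed/other category rather than test it is also a scientific decision that the investigators should own.

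Raising VI.1 to 120 would also reconcile the figures, but I would not ask for it. At the 7 to 10 hours per subject given in VII.E.6, 20 more people means 140 to 200 subject-hours (20 × 7 to 20 × 10), for a gain of about 0.06 SD in a pilot with no precision target.

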## **XII. Future Research**

**XII.1** *Do you wish to keep any information about subjects involved with this research project so that members of the current research team may contact them in the future for your own research projects?*  
Yes

**XII.2** *Do you wish to keep any information about subjects involved with this research project so that [other researchers](#) may contact them for future research?*  
No

**XII.3** *List the data or information you will keep:*  
Information from the screening log will be kept only for those individuals who have consented to participate in the study.

**XII.4** *Does this project involve storing any data, tissues or specimens for future research?*

Yes – contribution for future use is mandatory for participation in the study
